6. STUDY DRUG

6.1 Description of Investigational Agents

Ixazomib Capsules

The ixazomib drug product is provided in strengths of 4.0-, 3.0-, and 2.3-mg capsules as the active boronic acid. The different dose strengths are differentiated by both capsule size and color as described below:

Dose Strength	Capsule Size	Capsule Color
4.0 mg	Size 4	Ivory
3.0 mg	Size 3	Light gray
2.3 mg	Size 2	Light pink

For additional details, please see the ixazomib IB.

6.2 Study Drug Administration

Ixazomib Administration

All protocol-specific criteria for administration of study drug must be met and documented before drug administration. Study drug will be administered or dispensed only to eligible patients under the supervision of the investigator or identified subinvestigator(s). Patients should be monitored for toxicity, as necessary, and doses of ixazomib should be modified as needed to accommodate patient tolerance to treatment; this may include symptomatic treatment, dose interruptions, and adjustments of ixazomib dose (see Section 6.3).

Capsules of ixazomib will be supplied by Millennium as capsules of 2.3-, 3.0- and 4.0 mg ixazomib.

The prescribed administration of ixazomib doses in this study is 4mg ixazomib in a 28 day cycle.

Patients should be instructed to swallow ixazomib capsules whole, with water, and not to break, chew, or open the capsules. Ixazomib should be taken on an empty stomach (no food or drink) at least 1 hour

before or at least 2 hours after food. Each capsule should be swallowed separately with a sip of water. A total of approximately 8 ounces (240 mL) of water should be taken with the capsules.

Missed doses can be taken as soon as the patient remembers if the next scheduled dose is 72 hours or more away. A double dose should not be taken to make up for a missed dose. If the patient vomits after taking a dose, the patient should not repeat the dose but should resume dosing at the time of the next scheduled dose.

Ixazomib Destruction

Investigational ixazomib (expired or end of study) should be destroyed on site according to the institution's standard operating procedure. Be sure to document removal and destruction on drug accountability logs.

Standard of Care Therapies

6.2.2 Thalidomide Administration

Thalidomide will be provided as a standard of care therapy via the PBS. Therefore all patients will need to be registered in, and abide by, the requirements of the i-access® Risk Management Program. Thalidomide will be given as a single, daily oral dose of 100mg for 28 days out of the 28-day cycle. No dose reduction will be made for impaired creatinine clearance. Administration of thalidomide will be approximately the same time each day. Patients should be instructed to swallow thalidomide capsules whole with or without food and not to break, chew, or open the capsules. If a dose of thalidomide is missed, it should be taken as soon as possible on the same day. If it is missed for the entire day, it should not be made up.

Patients who take more than the prescribed dose of thalidomide should be instructed to seek emergency medical care if needed and contact study staff immediately.

6.2.3 Dexamethasone Administration

Dexamethasone will be given as an oral dose of 40 mg/day weekly on Days 1, 8, 15, and 22 of a 28-day cycle.

Dexamethasone should be taken at approximately the same time preferably with food/milk to avoid stomach irritation. If a dose of dexamethasone is missed, the dose should be taken as soon as the patient remembers it. If enough time has elapsed that it is almost time for the next dose (within 72 hours), the missed dose should be skipped and the next dose taken according to the regular dosing

schedule. A double dose should not be taken to make up for a missed dose. If the patient vomits after taking a dose, the patient should not repeat the dose but should resume dosing at the time of the next scheduled dose.

All patients should receive acid reflux prophylaxis (ie pantoprazole 40mg daily) as per institutional protocol

6.2.4 Thromboembolic prophylaxis as per institutional protocol

Clinical studies with thalidomide in combination with dexamethasone as well as other chemotherapeutic agents have shown an increase in risk of VTE. Aspirin or LMWH has been reported to be effective in reducing the incidence of DVT in myeloma patients treated with thalidomide.

For this study, all patients will receive anti-thrombotic prophylaxis, either aspirin 100mg daily or prophylactic doses of LMWH according to hospital guidelines or physician preference. All patients will be monitored for signs and symptoms of VTE while on study treatment. Those patients in whom anti-thrombotic prophylaxis is contraindicated (or refused by the patient) will be excluded from the study.

6.2.5 Anti-viral prophylaxis as per institutional protocol

All patients should be commenced on anti-viral prophylaxis for the prevention of reactivation of herpes at the study commencement (i.e. on or before cycle 1 day 1).

6.2.6 Bisphosphonate prophylaxis as per institutional protocol

Bisphosphonate prophylaxis for bone protection (ie zoledronic acid 4mg iv monthly) is recommended as per institutional protocol.

6.3 Dose-Modification Guidelines

Causality of adverse events will be assigned by the treating clinician at the time of occurrence and dose-modifications undertaken accordingly. Where there is an overlap of toxicity profile, dose reduction of offending agent as determined by the treating clinician will be undertaken. For example; myelosuppression (haematological AE) would result in dose reduction of ixazomib in the first instance, whereas peripheral neuropathy would result in dose reduction of thalidomide initially.

6.3.1 Recommended Ixazomib, Thalidomide and Dexamethasone Criteria for Beginning or Delaying a Subsequent Treatment Cycle & Dose Modifications for Treatment Associated Toxicity

Treatment with the combination of ixazomib/thalidomide/dexamethasone will use a cycle length of 28 days. For a new cycle of treatment to begin, the patient must meet the following criteria:

- ANC must be $\geq 1,000/\text{mm}^3$.
- Platelet count must be $\geq 75,000/\text{mm}^3$.
- All treatment-related non-hematologic toxicity (except for alopecia) must have resolved to \leq Grade 1 or to the patient's baseline condition except for isolated gamma glutamyl transferase (GGT) elevations.

If the patient fails to meet the above-cited criteria for initiation of the next cycle of treatment, dosing should be delayed for 1 week. At the end of that time, the patient should be re-evaluated to determine whether the criteria have been met. If the patient continues to fail to meet the above-cited criteria, delay therapy and continue to re-evaluate. The maximum delay before treatment should be discontinued will be 3 weeks or at the discretion of the Principal Investigator.

For dosing recommendations upon recovery, refer to Table 6-2 and Table 6-3.

Table 6-1 Ixazomib Dose Adjustments

Dose Level	Dose (mg)
Starting Dose	4.0 mg
-1	3.0 mg
-2	2.3 mg
-3	Discontinue

Note: If ixazomib is discontinued patients may continue thalidomide and dexamethasone and therefore remain on study.

Dosage adjustments for hematologic toxicity are outlined in Table 6-2.

Table 6-2 **Ixazomib and Thalidomide** Dose Adjustments for Hematologic Toxicities

Criteria	Action
Within-Cycle Dose Modifications	

 If platelet count $\leq 30 \times 10^9/L$, ANC $\leq 0.50 \times 10^9/L$ on any dosing day other than Day 1). ANC $\leq 1.0 \times 10^9/L$ with fever at any time during a cycle. 	
Ixazomib, thalidomide and dexamethasone dose should be withheld.
 
Complete blood count (CBC) with differential should be repeated at least every other day until the ANC and/or platelet counts have exceeded the prespecified values (see Section 6.3.1) on at least 2 occasions. Or at physician's discretion if G-CSF is used for neutropenia.
 
Upon recovery ixazomib be reinitiated with 1 dose level reduction.
 
During the 2nd observation of thrombocytopenia, thalidomide should be reinitiated at 1 dose level reduction, and continue alternating dose reductions whilst the patient is on treatment

Dose Modifications for Subsequent Treatment Cycles	

 Delay of > 2 weeks in the start of a subsequent cycle due to lack of toxicity recovery as defined in Section 6.3.1: as follow: ANC $< 1.0 \times 10^9/L$, platelet count $< 75 \times 10^9/L$, or other nonhematologic toxicities > Grade 1 or not to the patient's baseline condition 	
Hold ixazomib and thalidomide until resolution as per criteria Section 6.3.1.
 
Upon recovery thalidomide should be reinitiated with 1 dose level reduction (if ixazomib was already reduced during the preceding cycle. Continue alternating dose reductions whilst the patient is on treatment.
 
The maximum delay before treatment should be discontinued will be 3 weeks or at the discretion of the PI.

Treatment modifications due to ixazomib and/or thalidomide-related AEs are outlined in Table 6-3.

Table 6-3 **Ixazomib/Thalidomide** Treatment Modification (Delays, Reductions, and Discontinuations) Due to Adverse Events (Non-Hematologic Toxicities)

Adverse Event (Severity)	Action on Ixazomib and Thalidomide	Further Considerations
Peripheral Neuropathy:		
Grade 1 peripheral neuropathy without pain	
 No action 	Grade 1 signs and symptoms: asymptomatic; without pain or loss of function; clinical or diagnostic observations only (19)
New or worsening Grade 1 peripheral neuropathy with pain or Grade 2	
 Hold ixazomib and thalidomide until resolution to Grade \leq 1 without pain or baseline 	Grade 2 signs and symptoms: Moderate symptoms; limiting instrumental activities of daily living (ADL) (19)
New or worsening Grade 2 peripheral neuropathy with pain or Grade 3	
 Hold ixazomib and thalidomide until resolution to Grade \leq 1 or baseline Reduce thalidomide to next lower dose upon recovery. During the 2nd observation of new or worsening Grade 2 peripheral neuropathy with pain or Grade 3, ixazomib should be reinitiated at 1 dose level reduction, and continue alternating dose reductions whilst the patient is on 	Grade 3 signs and symptoms: severe symptoms; limiting self-care ADL; assistive device indicated (19)

Table 6-3 **Ixazomib/Thalidomide** Treatment Modification (Delays, Reductions, and Discontinuations) Due to Adverse Events (Non-Hematologic Toxicities)

Adverse Event (Severity)	Action on Ixazomib and Thalidomide	Further Considerations
New or worsening Grade 4 peripheral neuropathy	
 Discontinue ixazomib and thalidomide Dexamethasone therapy may be continued 	
Grade 2 Rash	
 Symptomatic recommendations as per section 6.7 	The investigator may consider dose modifications and symptom management.
Grade 3 nonhematologic toxicity judged to be related to ixazomib and/or thalidomide (including Grade 3 rash)	
 Hold ixazomib and thalidomide (and dexamethasone if thought by clinician to be a possible causative agent) until resolution to Grade \leq 1 or patient's baseline Reduce implicated study drug (ixazomib, thalidomide or dexamethasone) to next lower dose upon return to \leq Grade 1 or patient's baseline (investigator discretion, consider dose reduction if delay of >2 weeks to recovery to these values). 	Symptomatic recommendations noted in Section 6.7

Table 6-3 **Ixazomib/Thalidomide** Treatment Modification (Delays, Reductions, and Discontinuations) Due to Adverse Events (Non-Hematologic Toxicities)

Adverse Event (Severity)	Action on Ixazomib and Thalidomide	Further Considerations
Subsequent recurrence Grade 3 nonhematologic toxicity	
 • Hold study drugs (ixazomib, thalidomide and dexamethasone) until resolution to Grade 1 or patient’s baseline • Reduce implicated study drug (ixazomib, thalidomide or dexamethasone) to next lower dose (investigator discretion, consider dose reduction if delay of >2 weeks to recovery to these values). 	Monitor closely, take appropriate medical precautions, and provide appropriate symptomatic care
Grade 4 nonhematologic toxicities judged to be related to ixazomib and/or thalidomide	
 • Consider permanently discontinuing ixazomib and/or thalidomide 	Exceptions are cases in which the investigator determines the patient is obtaining a clinical benefit

Once any study drug/s is/are reduced for any toxicity, the dose may not be re-escalated. If any of ixazomib, thalidomide or dexamethasone is discontinued permanently patients may remain on study with the remaining agent/s.

For other side effects (ie constipation) symptomatic management (aperients etc.) should be attempted prior to a dose reduction.

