6.3.2 Recommended Dose Modifications for Thalidomide Treatment Associated Toxicity

Dosage adjustments for thalidomide are outlined in Table 6-4. Treatment modifications due to thalidomide-related AEs are outlined in Table 6-5.

Table 6-4 Thalidomide Treatment Modifications

Dose level	Daily, days 1-28 of 28 day cycle
Starting dose	100mg
-1	50mg
-2	Discontinue

For other side effects attributed to thalidomide (ie constipation) symptomatic management (aperients etc.) should be attempted prior to a dose reduction

Recommended Dose Modifications for Dexamethasone Treatment Associated Toxicity

Dosage adjustments for dexamethasone are outlined in Table 6-6

Table 6-5 Dexamethasone Treatment Modifications

Dose level	Weekly, days 1, 8, 15, 22 of 28 day cycle
Starting dose	40mg
-1	20mg
-2	8mg
-3	4mg
-4	Discontinue

Dose reduction of dexamethasone to a minimum of 4mg weekly will be allowed to manage toxicities. Dexamethasone should be discontinued if patient is unable to tolerate 4mg dose. Patients intolerant of dexamethasone 4mg weekly can continue on ixazomib and thalidomide therapy.

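### In Table 6-3, painful Grade 2 peripheral neuropathy meets two rows with different instructions for thalidomide on recovery, and the surrounding text and table references do not settle which applies.

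*Protocol*

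**What the plan says.** Section 6.3 leaves attribution to the clinician: where toxicities overlap, "dose reduction of offending agent as determined by the treating clinician will be undertaken". It illustrates this with two examples, the second being that neuropathy acts on thalidomide first: "whereas peripheral neuropathy would result in dose reduction of thalidomide initially". No grade is attached.

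Section 6.3.1 says where the restart dose is to be found: "For dosing recommendations upon recovery, refer to Table 6-2 and Table 6-3". The sentence that introduces Table 6-3 also assigns adverse events related to ixazomib or thalidomide to that table.

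The peripheral neuropathy part of Table 6-3 has four rows:

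- Grade 1 without pain: no action.
- "New or worsening Grade 1 peripheral neuropathy with pain or Grade 2": the only action is a hold of both drugs until resolution (the cell begins "Hold ixazomib and thalidomide until resolution to Grade"). No restart dose is given.
- "New or worsening Grade 2 peripheral neuropathy with pain or Grade 3": a hold, then thalidomide goes down one level on recovery. At a second such event ixazomib is reduced, and reductions alternate after that.
- Grade 4: both drugs are discontinued.

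Below the table: "Once any study drug/s is/are reduced for any toxicity, the dose may not be re-escalated".

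Section 6.3.2 gives the thalidomide ladder in Table 6-4 (100 mg, 50 mg, discontinue). It then states: "Treatment modifications due to thalidomide-related AEs are outlined in Table 6-5". Table 6-5 is the dexamethasone ladder (40, 20, 8, 4 mg, discontinue). Dexamethasone adjustments are referred to a Table 6-6, which appears neither in the text nor in the list of tables.

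**The concern.** A dose-modification table should give one action for each event. Here the Grade 2 limb of the second row is not restricted to painless events, so painful Grade 2 falls in that row and also in the third. The two rows differ on the point that matters at restart: one states a thalidomide reduction and the other is silent.

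The text around the table does not settle the question. The example in Section 6.3 carries no grade, so a site could take it as requiring a reduction even where the second row states none. A site that turns to the thalidomide section for help is sent to the dexamethasone table.

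Two reported results depend on this. Section 7.1.7 singles out peripheral neuropathy of Grade 2 or higher for particular attention. Section 3.1 makes total dose and percentage of planned dose (PPD) of each drug the tolerability endpoints alongside the co-primary safety endpoints. In a multi-centre trial of 45 patients, part of the variation in thalidomide PPD could reflect how each site reads the table and not how patients tolerate the drug.

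**Working it through.** **Step 1. Which row does each combination meet, taking the wording literally?**

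| Event (new or worsening) | Table 6-3 rows met | Thalidomide instruction after the hold |
|---|---|---|
| Grade 1, no pain | first | no hold, no action |
| Grade 1, pain | second | none stated |
| Grade 2, no pain | second | none stated |
| Grade 2, pain | second and third | none stated (second); reduce one level (third) |
| Grade 3 | third | reduce one level |

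One combination, Grade 2 with pain, has two entries. Two others, painful Grade 1 and painless Grade 2, have one row each but no restart instruction in it, although Section 6.3.1 names Tables 6-2 and 6-3 as the place to find one.

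**Step 2. Does Table 6-2 fill the gap?** Only in part. Its route for non-haematologic toxicity above Grade 1 applies when the next cycle is delayed by more than 2 weeks, and it reduces thalidomide if ixazomib was already reduced in the preceding cycle. For a first neuropathy event with ixazomib at full dose it states no thalidomide reduction.

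**Step 3. Table references.** Section 6.3.1 assigns thalidomide-related events to Table 6-3, while Section 6.3.2 assigns them to Table 6-5. By its title and content Table 6-5 is for dexamethasone. The list of tables ends at 6-5, so the reference to Table 6-6 has no target.

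**Step 4. What the reading can do to PPD.** Section 7.1.7 defines PPD as dose delivered divided by planned dose, as a percentage, reported by cycle and over the first 4 cycles. Inputs: 100 mg daily for 28 days (Section 6.2.2); next level 50 mg (Table 6-4). Hold days are ignored.

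- Planned per cycle: 100 × 28 = 2,800 mg. Over 4 cycles: 4 × 2,800 = 11,200 mg.
- At the reduced level: 50 × 28 = 1,400 mg per cycle, so PPD = 1,400 / 2,800 = 50%. Restarted at 100 mg it is at most 100%.
- Four-cycle PPD, reduced from cycle 2: (2,800 + 3 × 1,400) / 11,200 = 7,000 / 11,200 = 62.5%.
- Reduced from cycle 3: (5,600 + 2 × 1,400) / 11,200 = 8,400 / 11,200 = 75%.
- Reduced from cycle 4: (8,400 + 1,400) / 11,200 = 9,800 / 11,200 = 87.5%.

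These are figures for a single patient. The protocol states no figure of its own on this point to reproduce.

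**The case against.** The strongest reply is that the documents can be read without conflict. The clause in Section 6.3 is introduced as an example of clinician attribution. It tells the reader which drug goes first once a reduction is due, not that one is due. Read as a trigger for any neuropathy, it would also contradict the no-action row for painless Grade 1, so it was probably not meant that way. The third row carries the example out: thalidomide first, ixazomib at the second event. The rows rise in severity, and the third names painful Grade 2 expressly, so the specific row could be taken to govern and the second to cover the remainder. The wrong references look like numbering slips, and Section 6.3.1 already gives the correct pointer. PPD is descriptive, has no decision threshold, and records what was delivered whichever row is followed.

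Much of this stands. A reader might infer a three-way conflict in which 6.3, Table 6-3 and 6.3.2 each fix a different thalidomide dose. The documents do not support that. The 6.3 clause has no grade, the second row is silent and does not say that the dose is unchanged, and no thalidomide dose can be taken from a dexamethasone ladder.

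The overlap itself is not answered. That the specific row governs is a sensible convention, but the protocol does not state it, and it would still leave painless Grade 2 and painful Grade 1 without a restart instruction in the table that Section 6.3.1 names for that purpose.

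**Conclusion.** The point holds in a limited form. Table 6-3 assigns two different thalidomide instructions to painful Grade 2 neuropathy. The second neuropathy row gives no restart dose. The ungraded example in Section 6.3 can be read as supplying a reduction there. Two table references in 6.3.2 are wrong.

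For an affected patient the reading can change thalidomide PPD from up to 100% to 50% in each later cycle, or to between 62.5% and 87.5% over the first four cycles if the reduction begins at cycle 2, 3 or 4. This assumes that hold days are ignored and that no further modification occurs.

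Two stronger inferences should be resisted. The first is that the reading fixes a patient at 100 mg for the rest of treatment. The bar on re-escalation makes only a reduction lasting; a patient restarted at 100 mg can still be reduced after a later event. The second is to apply the 26% neuropathy rate in Table 1-3 to the 45 patients. That rate is for any grade and comes from combinations with lenalidomide-dexamethasone or melphalan-prednisone, not thalidomide, so it does not count patients who would meet these rows. The number affected cannot be derived from the protocol.

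This is more than a typographical matter because the rows are an operative safety instruction for a toxicity that the safety analysis singles out. No view is taken here on which dose rule is right.

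**What to change.** Reconcile Section 6.3 with the neuropathy rows of Table 6-3 so that each combination of grade and pain falls in exactly one row, and each row states the restart instruction for each drug. If the example in 6.3 is meant only to set the order of reduction, say so. What the instruction should be is a clinical decision for the sponsor.

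Correct Section 6.3.2 so that thalidomide-related events point to the table that governs them, consistent with Section 6.3.1, and so that dexamethasone adjustments point to Table 6-5.

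The cost is protocol wording in 6.3, Table 6-3 and 6.3.2. No additional patients, visits or data are needed.

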6.3.2 Recommended Dose Modifications for Thalidomide Treatment Associated Toxicity

Dosage adjustments for thalidomide are outlined in Table 6-4. Treatment modifications due to thalidomide-related AEs are outlined in Table 6-5.

Table 6-4 Thalidomide Treatment Modifications

Dose level	Daily, days 1-28 of 28 day cycle
Starting dose	100mg
-1	50mg
-2	Discontinue

For other side effects attributed to thalidomide (ie constipation) symptomatic management (aperients etc.) should be attempted prior to a dose reduction

Recommended Dose Modifications for Dexamethasone Treatment Associated Toxicity

Dosage adjustments for dexamethasone are outlined in Table 6-6

Table 6-5 Dexamethasone Treatment Modifications

Dose level	Weekly, days 1, 8, 15, 22 of 28 day cycle
Starting dose	40mg
-1	20mg
-2	8mg
-3	4mg
-4	Discontinue

Dose reduction of dexamethasone to a minimum of 4mg weekly will be allowed to manage toxicities. Dexamethasone should be discontinued if patient is unable to tolerate 4mg dose. Patients intolerant of dexamethasone 4mg weekly can continue on ixazomib and thalidomide therapy.

6.4 Excluded Concomitant Medications and Procedures

The following medications and procedures are prohibited during the study.

Systemic treatment with any of the following metabolizing enzyme inducers should be avoided, unless there is no appropriate alternative medication for the patient's use (Rationale: If there were to be a drug-drug interaction with an inducer, ixazomib exposure would be decreased:

- Strong CYP3A inducers: rifampin, rifapentine, rifabutin, carbamazepine, phenytoin, and phenobarbital

The following medicinal products and procedures are prohibited during the study.

- Excluded foods and dietary supplements include St. John's wort and Ginkgo biloba

- Any antineoplastic treatment with activity against MM, other than study drugs
- Radiation therapy (note that, in general, the requirement for local radiation therapy indicates disease progression)
- Platelet transfusions to help patients meet eligibility criteria are not allowed within 3 days prior to study drug dosing for any dosing day.

